4.5 Patient stratification

Subjects will be stratified according to sidedness⁵ and (K)RAS/BRAF mutation status of the primary tumor (right-sided *versus* left-sided and (K)RAS/BRAF wild-type *versus* mutation) of two reasons. Firstly, patients in good performance status (ECOG 0–1) with (K)RAS/BRAF wild-type tumor (which frequently is left-sided) will commonly and according to national guidelines be offered an irinotecan-containing regimen with the addition of an EGFR inhibitor. A block-randomization within each study stratum will ensure that this therapeutic option does not compromise enrolment onto any of the other groups (*c.f.*, [Paragraph 10.1](#)). Secondly, stratification will enable outcome analysis (PFS) within each of the defined groups, among which the study treatment may show differential effects. Ideally, tumor MSS status should be determined to avoid inclusion of MSI cases; however, the current logistics of this analysis at hospitals commonly

precludes it from being undertaken swiftly enough before the commencement of active therapy. In order to meet this challenge, tumor MSS status will be determined as per current practice. It is expected that approximately 5% of enrolled patients will harbor non-MSS tumor [Cancer Genome Atlas Network, 2012; Goldstein *et al.*, 2014], and the statistical power analysis (*c.f.*, [Paragraph 10.2.1](#)) has been adjusted to enable removal of these few cases before data analysis.

⁵ **Sidedness** is defined as follows: *right-sided*, primary tumor in cecum, ascending colon, or transverse colon; *left-sided*, primary tumor in splenic flexure, descending or sigmoid colon, or rectum.

4.6 Risk/benefit assessment

Study patients will in general benefit from follow-up of their disease and treatment within the frame of a prospective trial. Safety and efficacy for control arm patients (*c.f.*, [Paragraph 5.5](#)) are well known from a number of previous studies and routine clinical practice over two decades.

For experimental arm patients (*c.f.*, [Paragraph 5.5](#)), particular hazards and benefits may prevail. Patients suffering from MSS metastatic CRC do not possess an inherently immunogenic disease and may experience untoward effects from sequential nivolumab following the short-course treatment with FLOX. In addition, these patients will receive half the number of FLOX cycles over a defined treatment period compared to the standard-of-care. Each of these aspects may occasion detrimental treatment responses. Also, keeping in mind that the repeat sequential treatment is a novel design with no safety data known as of yet, new and unexpected toxicities may appear.

On the other hand, experimental arm patients will have an unprecedented opportunity to receive treatment, in terms of ICB, that is currently not available for the vast majority of patients with metastatic CRC. If the study hypothesis prevails and oxaliplatin treatment transforms MSS metastatic CRC into an immunogenic disease, there is an opportunity for durable treatment effects from the sequential ICB, similar to those observed with single-agent ICB in MSI metastatic CRC [Le *et al.*, 2015; Le *et al.*, 2017]. It is also conceivable that sequential ICB may dampen common side effects of the FLOX regimen, which might ultimately result in tolerability to a higher number of FLOX cycles than usual for the standard-of-care.

5 TREATMENT

For this study, nivolumab (Opdivo®), oxaliplatin, 5-fluorouracil, and folinic acid (Leucovorin) are defined as IMP.

5.1 Drug handling

With regard to nivolumab, the drug will be provided by Bristol-Myers Squibb (BMS) as flat dosing kits, each containing 240 mg of the drug (two vials of 100 mg each and one vial of 40 mg). In the event of availability constraints of 40-mg vials, 100-mg vials will be provided for dispense. The Hospital Pharmacy of Mid Norway Trust (Sykehusapoteket, Trondheim) will be used as vendor to provide import, labeling, storage, and dispatch of the drug from BMS to each participating center in Norway in accordance with the environmental conditions (temperature, light, humidity) as determined by BMS. At each center, the product storage manager at the study pharmacy will ensure that nivolumab is stored and dispensed in accordance with these conditions. If concerns regarding the quality or appearance of nivolumab arise, the study drug will not be dispensed and BMS will be contacted immediately. Please refer to the BMS IB for nivolumab regarding drug-related information such as handling, storage, infusion, *etc.*

At each center, oxaliplatin, 5-fluorouracil, and folinic acid will be provided by the study pharmacy as per routine practice.

IMP documentation will be maintained. This includes all processes required to ensure that the drugs are accurately administered. Also, it includes documentation of drug storage, administration, and, as applicable, storage temperatures, reconstitution, and use of required processes (*e.g.*, diluents, administration sets).

Infusion-related supplies (*e.g.*, bags, in-line filters, 0.9% sodium chloride injection, 5% dextrose injection) will be supplied by each study site and purchased locally if permitted by local regulations.

The IMPs will be stored in a secure area according to local regulations. It is the responsibility of the investigators to ensure that IMPs are only dispensed to study subjects. The IMPs will be dispensed only from official study sites by

authorized personnel according to local regulations. Please refer to the current IB version and/or pharmacy reference sheets for complete storage, handling, dispensing, and infusion information for nivolumab. The infusion will be administered by nurses with experience in treatment with immunotherapy.

The Nordic FLOX regimen is standard-of-care; thus, drug administration will be according to each participating department's standard operating procedure (SOP). Likewise, expenses for the actual drugs and their administration will be covered by the participating departments' standard budget.

5.2 Drug accountability

The responsible site personnel will confirm receipt of study drug and will use the study drug only within the framework of this study and in accordance with this protocol. Receipt, distribution, and destruction (if any) of the study drug will be properly documented according to Sponsor's agreed and specified procedures. Any destruction of nivolumab will be reported back to BMS.

Pertaining to each of the study drugs, Clinical Investigator will prescribe the actual dose and treatment cycle in sufficient detail within a predefined study-specific form in the Hospital's electronic prescription system. Each prescription will be documented in an electronic logbook at the study pharmacy, which will identify which study patient has received which study drug (name, dose, batch number, shelf life, and amount). The study pharmacy will apply procedures that guarantee the traceability of this information.

5.3 Drug labeling

The IMP (nivolumab), as dispatched from the Hospital Pharmacy of Mid Norway Trust, will have a label permanently affixed to the outside of the vials/kits and will be labeled according with ICH GCP and national regulations, stating that the material is for clinical trial / investigational use only and should be kept out of reach of children.

Labeling of IMP should be done according to Eudralex volume 4, Annex 13 (http://ec.europa.eu/health/files/eudralex/vol-4/2009_06_annex13.pdf).

For Norway, labeling is required according to Chapter 4.4 in "Forskrift om klinisk utprøving av legemidler til mennesker" (<http://www.lovdata.no/for/sf/ho/xo-20091030-1321.html>). However, because the infusion bags for all four IMPs will be dispensed and administered by authorized personnel at the study sites, immediately following the prescription by Clinical Investigator, the Norwegian Medicines Agency is entitled to make an exception from the labeling requirements. Nevertheless, all IMP bags will have an affixed label with blank lines for:

- patient's initials
- patient's enrolment code
- protocol code
- date dispensed
- name of prescribing doctor
- name of Principal Investigator

5.4 Dosage, drug administration, and common toxicities

FLOX: oxaliplatin 85 mg/m² (over 30–60 minutes) on day 1; bolus (over <5 minutes) 5-fluorouracil 500 mg/m² and 30 minutes later bolus (over <10 minutes) folinic acid on days 1 and 2; IV administration every 2 weeks.

Common toxicities are acute allergic reactions (laryngopharyngeal dystonia, anaphylaxis), moderate nausea and vomiting, diarrhea, hand-foot-syndrome, hyperpigmentation, mucositis, fatigue, neuropathy, febrile neutropenia, and thrombocytopenia.

Nivolumab: 240 mg flat dose over 30 minutes, IV administration every 2 weeks.

In general, the use of ICB leads to a unique spectrum of side effects termed immune-related AE (irAE) or, occasionally, AE of special interest. The irAE include dermatologic, gastrointestinal, hepatic, endocrine, and other less common inflammatory events. These are believed to arise from general immunologic enhancement. Temporary immune suppression with corticosteroids, tumor necrosis factor-alpha antagonists, mycophenolate mofetil, or other agents can be an effective treatment in most cases.

5.5 Duration of therapy

The **control arm** will consist of intermittent treatment with the Nordic FLOX regimen in terms of 8 cycles (16 weeks) before a break until disease progression, when therapy is reintroduced and administered for another 8 cycles before a new break. This go-and-stop schedule, which is chosen because continuous FLOX treatment commonly causes unacceptable toxicity in the palliative setting, will be continued until progressive disease on ongoing therapy (defining PFS in terms of failure of treatment strategy), unacceptable toxicity, withdrawal of consent, or death, whichever occurs first.

The estimated median PFS in the control arm is 9 months (*i.e.*, 39 weeks), as detailed in [Chapter 10](#). During this period, it is assumed that the ‘average’ patient will receive 1 full go-and-stop treatment sequence, consisting of 16 weeks of active therapy followed by 8 weeks of break until disease progression, before the second treatment period results in progressive disease after 16 weeks on ongoing therapy; hence, a PFS of 40 weeks. During the entire treatment, this patient will receive 2 sequences of active therapy, each containing 8 FLOX cycles.

The **experimental arm** will consist of repeat 2 cycles of the Nordic FLOX regimen followed by 2 cycles of nivolumab for a total of 8 individual cycles (16 weeks) before a break until disease progression, when therapy is reintroduced and administered for another total of 8 individual cycles before a new break. This go-and-stop schedule will be continued until progressive disease on ongoing therapy (defining PFS in terms of failure of treatment strategy), unacceptable toxicity, withdrawal of consent, or death, whichever occurs first.

[figure not shown]

Figure 4 – the experimental treatment arm.

The estimated median PFS in the experimental arm is 18 months (*i.e.*, 78 weeks), as detailed in [Chapter 10](#). During this period, it is assumed that the ‘average’ patient will receive 3 full go-and-stop treatment sequences, each consisting of 16 weeks of active therapy followed by 8 weeks of break until disease progression, before the fourth treatment period results in progressive disease after 8 weeks on ongoing therapy; hence, a PFS of 80 weeks. During the entire treatment, this patient will receive 4 sequences of active therapy, each containing 4 cycles each of FLOX and nivolumab.

The optimum duration of immune-modulating therapy is currently unknown. However, because such therapy engages the immune system to control the tumor, continuous treatment, as is required with other types of biologically targeting agents or systemic cytotoxic therapies, may not be necessary.

Accumulating evidence from different clinical trials in different tumor types with nivolumab or nivolumab combined with the ICB drug ipilimumab indicates that most of the responses are generally occurring early, with a median time to response of 2–4 months [Brahmer *et al.*, 2015; Borghaei *et al.*, 2015; Hellmann *et al.*, 2016; Larkin *et al.*, 2015; Motzer *et al.*, 2015]. A recent analysis in a melanoma study suggests the majority of patients who discontinue nivolumab and/or ipilimumab for toxicity maintain disease control in the absence of further treatment (Schadendorf D *et al.*, reported at the 2016 Annual Meeting of the European Association of Dermato-Oncology in Vienna, Austria). Furthermore, a limited duration of ipilimumab including only 4 induction doses resulted in long-term survival in patients with metastatic melanoma, with a sustained plateau in survival starting at around year 3 [Schadendorf *et al.*, 2015].

For these reasons, in the present study, a total of 24 months of active sequential FLOX and nivolumab therapy will be administered, given the absence of disease progression (while the subject is on active therapy) or unacceptable toxicity at an earlier treatment time. After 24 months, FLOX alone may be administered as per the study dosing schedule in the control arm. Experimental arm subjects who complete a total of 24 months of active sequential FLOX and nivolumab therapy and have subsequent disease progression (on or off FLOX alone) may, at the discretion of Clinical Investigator, reinstitute sequential FLOX and nivolumab at the same dose and schedule given previously on study, and continue such treatment for up to 1 additional year. Continuation of treatment with FLOX beyond a total of 24 months of active sequential FLOX and nivolumab therapy (*i.e.*, 12 months of active FLOX) is contingent on continued tolerance for FLOX.

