2 STUDY OBJECTIVES AND END POINTS

Hypothesis: Most patients with metastatic CRC harbor tumor that can be transformed into an immunogenic disease by oxaliplatin, and may thereby benefit from the addition of immune-modulating therapy to improve outcome of the current oxaliplatin-based standard-of-care.

	Objectives	End points
Primary	
To determine PFS, in terms of failure of treatment strategy, on sequential treatment with the Nordic FLOX regimen and nivolumab² compared with the standard-of-care Nordic FLOX regimen in previously untreated MSS metastatic CRC.
 
² Nivolumab is an ICB agent.
	
 – PFS: radiologic assessment every 8 weeks (following 4 cycles of FLOX or the alternative 2 cycles each of FLOX and nivolumab), according to the Response Evaluation Criteria in Solid Tumors (RECIST) and the RECIST consensus guideline for assessment of response to immune-modulating therapies, iRECIST (c.f., Appendices 1 and 2).
Secondary	
To determine safety and tolerability of sequential treatment with the Nordic FLOX regimen and nivolumab compared with the standard-of-care Nordic FLOX regimen.
 
To determine objective response rate (ORR), duration of response (DOR), secondary surgical curative resection rate (SSCRR), and OS.
	
 – Safety: incidence of adverse events (AE), as reported according to Common Terminology Criteria for Adverse Events (CTCAE) version 4.0 (c.f., Appendix 3) recorded on onboing basis, and summarized every 4 weeks on active study therapy and every 8 weeks in planned breaks from active study therapy. – Tolerability: AE grading, as assessed by CTCAE v4.0 recorded on onboing basis, and summarized every 4 weeks on active study therapy and every 8 weeks in planned breaks from active study therapy. – ORR: the percentage of patients with a confirmed complete or partial response. – DOR: the time from the first documentation of a complete or partial response to disease progression. – SSCRR: the percentage of patients with a confirmed resection of metastatic disease with microscopically free margin (R0). – OS: the time from randomization to death of any cause.

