7.6 Tumor imaging and assessment of disease procedures

7.6.1 Evaluation of efficacy

The imaging assessments will be performed by CT, typically a thoracic/abdominal/pelvic CT scan. Tumor treatment response will be assessed according to RECIST v1.1 as the primary method and iRECIST as the secondary method. After baseline tumor assessments, evaluation of tumor response will be performed every 8 weeks (± 7 days). Additional MR scans or other radiologic evaluations will be performed if indicated.

All radiologic examinations will be transmitted to Study Radiologist at Akershus University Hospital within 1 working day after the scan is performed. A radiologist at the actual study center will evaluate the images for incidental findings that may have a therapeutic consequence (e.g., pulmonary embolism, immune therapy-related findings that require emergency actions).

Study Radiologist will be blinded to patient treatment, but will be informed about treatment breaks in the go-and-stop schedule. Study Radiologist will primarily assess tumor measures according to RECIST v1.1. If disease progression is concluded by means of RECIST v1.1, Study Radiologist will also assess tumor measures according to iRECIST. The radiology report will detail the criteria used for Clinical Investigator to make a decision about further study treatment (*c.f.*, [Paragraph 5.7.2.4](#)).

PFS will be calculated from the day of randomization to first recorded disease progression according to RECIST v1.1 or iRECIST when applicable, or death. Patients who have not had disease progression at the time of final analysis will be censored at the date last known to be alive and progression-free.

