7.6.5 Frequency of tumor re-evaluation

Frequency of tumor re-evaluation will be every 8 weeks in both arms and during planned study treatment breaks. In the case of suspected clinical progression or iUPD according to iRECIST, the next evaluation may be preponed to after 4 weeks.

Evaluation will be with routine CT of the thoracic/abdominal/pelvic cavities, preferably with contrast in the case of adequate renal function.

If brain or bone metastasis is suspected, supplemental MR evaluations may be undertaken. However, bone scans only need to be repeated when CR is identified in target disease or when progression in bone is suspected.

All target and non-target sites are assessed at each evaluation.

After discontinuation of protocol treatment, patients who have not progressed will still be re-evaluated every 8 weeks until end-of-study, as per protocol.

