10 STATISTICAL METHODS AND DATA ANALYSIS

10.1 Determination of sample size

Calculation of sample size was performed for PFS – the primary end point – and based on PFS data from recent publications. A median PFS of 9 months was assumed for the standard-of-care (control arm) [Cartwright, 2012; Tveit *et al.*, 2012; Cremolini *et al.*, 2015]. Regarding the therapy concept of ICB, there is no PFS data published as yet for the setting of interest. In the study of patients with treatment-refractory metastatic CRC, median PFS was not reached in the cohort with mismatch repair-deficient disease at the time of reporting [Le *et al.*, 2015]. In the study of previously untreated patients with advanced non-small cell lung cancer, which is a tumor entity with considerably poorer prognosis than advanced CRC, patients with PD-L1-positive tumors that were randomized to ICB showed median PFS of 10.3 months compared to 6.0 months for standard chemotherapy [Reck *et al.*, 2016].

Extrapolating to the setting of interest, with a median PFS of 9 months for standard-of-care, a median PFS twice as long (18 months) was entered for the sequential therapy. Assuming the exponential distribution of survival functions, the median PFS estimates were converted to hazard ratio (HR) of 0.5. Allowing for 10% censoring rate of subjects, the required sample size was estimated to be 40 patients in each arm to be able to show that HR of 0.5, implying the risk of a PFS event in the experimental group is 50% lower than in the control group, is significantly different from 1 with the power of 80% at significance level of 5%, given that log-rank test will be used.

However, it was necessary with several adjustments of the above calculations to maintain sufficient power. First, the sample size was adjusted to enable removal of a maximum of 5% enrolled cases with non-MSS tumor before data analysis. Next, keeping in mind the condition of patients, it is not unlikely that some will be lost from the study before a valid PFS event has been reached. Also, a number of analyses stratified by primary tumor sidedness and (K)RAS/BRAF mutation status will be performed. Hence, to enable high enough power in the statistical analysis, the sample size was increased by an additional 20%. After incorporating the adjustments, the final sample size was estimated to be 100 patients, 50 in each arm, with 1:1 randomization.

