10.4 Statistical analysis of clinical end points

10.4.1 Main statistical analyses

The main statistical analysis is planned after the last patient has fulfilled the pre-defined follow-up period. PFS will be calculated from the day of randomization to first recorded disease progression according to RECIST v1.1 or when applicable iRECIST, or death. Patients who have not had disease progression at the time of final analysis will be censored at the date last known to be alive and progression-free. The analyses will compare the treatment groups in total as well as groups stratified by primary tumor sidedness and (K)RAS/BRAF mutation status.

Deviation from the original statistical plan will be described and justified in the clinical study report. Amendments to plan can be done until the day of database lock.

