### **1.2. Objectives**

*Primary objective:* To determine progression-free survival (PFS), in terms of failure of treatment strategy, on sequential treatment with the Nordic FLOX regimen and nivolumab compared with the standard-of-care Nordic FLOX regimen in previously untreated metastatic MSS-CRC.

*Secondary objectives:*

- i) To determine safety and tolerability of sequential treatment with the Nordic FLOX regimen and nivolumab compared with the standard-of-care Nordic FLOX regimen.
- ii) To determine objective response rate (ORR), duration of response (DOR), secondary surgical curative resection rate (SSCRR), and overall survival (OS).
- iii) To monitor and compare quality-of-life (QoL) alterations during therapy courses.

*Tertiary objective:* To compare costs for the resource use (in diagnostic work-up, treatment, and any adverse events) for the sequential therapy with that of the standard-of-care, applying a model specifically developed for CRC.

*Exploratory objectives:*

- i) To develop circulating biomarkers of cytotoxic T lymphocyte activity.
- ii) To develop circulating biomarkers of tumor response.
- iii) To develop circulating biomarkers of immunogenic cell death.
- iv) To develop functional MR imaging biomarkers.
- v) To develop histologic and molecular tumor biomarkers.

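### The protocol and SAP define PFS in two incompatible ways, and the strategy-failure definition has no rule for progression that occurs off therapy

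*Protocol*

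**What the plan says.** **Strategy failure.** The primary objective in Protocol chapter 2 is "To determine PFS, in terms of failure of treatment strategy, on sequential treatment with the Nordic FLOX regimen and nivolumab" against FLOX alone, and SAP 1.2 repeats it: "To determine progression-free survival (PFS), in terms of failure of treatment strategy". Protocol 5.5 says what this means. In each arm the go-and-stop schedule ends at "progressive disease on ongoing therapy (defining PFS in terms of failure of treatment strategy), unacceptable toxicity, withdrawal of consent, or death, whichever occurs first". Here the parenthesis that defines PFS is attached to progression on therapy. Toxicity, withdrawal and death are listed as further reasons for the schedule to end. Progression during a planned break is followed by reintroduction of therapy and is not failure.

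**First progression.** Protocol 7.6.1 says "PFS will be calculated from the day of randomization to first recorded disease progression according to RECIST v1.1 or iRECIST when applicable, or death". Protocol 10.4.1 says the same, "PFS will be calculated from the day of randomization to first recorded disease progression according to RECIST v1.1 or when applicable iRECIST, or death", and SAP 5.2 repeats 10.4.1. None of the three requires the patient to be on therapy. The only censoring rule is that patients without progression at the final analysis "will be censored at the date last known to be alive and progression-free".

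**Assessment after treatment stops.** Protocol 7.6.5 says "patients who have not progressed will still be re-evaluated every 8 weeks until end-of-study, as per protocol". Protocol 7.7.3.2 gives 3-monthly visits in the first year after discontinuation. Protocol 7.7.4 follows disease status in patients who stop for reasons other than progression, but ends this when non-study cancer treatment starts. The flow chart in chapter 6 marks CT in the break period and at the end-of-study visit, and none in the post-treatment phase.

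**The concern.** The primary end point cannot be programmed from these documents without a choice that they do not make.

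Taken literally, SAP 5.2 scores a planned break progression as the event, although the treatment strategy expects that progression and continues after it. Taken literally, 5.5 leaves three groups without an event or censoring rule when their tumour grows:

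- patients who stopped for toxicity;
- patients who were resected (a secondary end point, with no PFS rule attached);
- patients who progressed in a break and were not restarted.

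An analyst working from 5.5 could censor these patients or count them only at death, although a patient who progresses in a break and cannot resume has failed the strategy in any ordinary sense. The control arm is scheduled for 8 FLOX cycles per sequence and the experimental arm for 4, so the frequency of these paths may differ by arm. The hazard ratio could then shift with the scoring choice.

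**Working it through.** **1. The plan's own sample size.** Inputs from Protocol 10.1: HR 0.5, 80% power, 5% level (taken as two-sided), log-rank test, 10% censoring. Freedman's formula gives events = (1.960 + 0.842)² × [(1 + 0.5)/(1 − 0.5)]² = 7.85 × 9 = 70.6, so 71. Then 71/0.90 = 78.9, or 40 per arm, as stated. The arithmetic is sound. The question is which event it counts.

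**2. Which definition the 5.5 courses fit.** Inputs from Protocol 5.5: 16 weeks on therapy, 8 weeks of break to progression.

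| Average patient | First recorded progression | Strategy failure |
|---|---|---|
| Control | 16 + 8 = week 24 | 16 + 8 + 16 = week 40 (stated median 9 months) |
| Experimental | 16 + 8 = week 24 | 3 × (16 + 8) + 8 = week 80 (stated median 18 months) |

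The courses that illustrate 9 v 18 months exist only under strategy failure. Under the calculation text both average patients have their event at week 24, with no difference between arms. This is an illustration in the protocol and not a distribution, and 10.1 does not say which PFS definition the cited publications used.

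**3. How many patients reach the restart decision.** With exponential PFS at the planned medians (39 and 78 weeks), the share failure-free at week 24 is 2^(−24/39) = 65% in control and 2^(−24/78) = 81% in the experimental arm. If 20% of them were not restarted (assumed), that is 13% and 16% of patients.

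**4. Scenario for the control median.** Assumptions: median 9 months when restarted; everyone failure-free at 5.5 months (week 24) progresses in the break then; 20% of them are not restarted, at random. S(5.5) = 2^(−5.5/9) = 0.655.

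- Scored as failure at that progression: the curve drops to 0.655 × 0.8 = 0.524. The median is 5.5 + 9 × log2(0.524/0.5) = 6.1 months.
- Censored at 3.7 months (week 16): S(3.7) = 0.752. The number at risk falls to 0.752 − 0.131 = 0.621, so the Kaplan-Meier value at 5.5 months is 0.752 × 0.524/0.621 = 0.634. The median is 5.5 + 9 × log2(0.634/0.5) = 8.6 months.
- Counted at death only (post-progression median 12 months, assumed): solving 0.655 × [0.8 × 2^(−u/9) + 0.2 × 2^(−u/12)] = 0.5 gives u = 3.7. The median is 9.2 months.

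Simulated trials of 50 per arm under the same assumptions give 6.3, 8.5 and 9.5 months.

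**5. Scenarios for the HR (simulation, same assumptions, 30-month cut-off).**

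| Median when restarted (control v experimental) | Not restarted (control v experimental) | HR, counted as failure | HR, censored or death only |
|---|---|---|---|
| 9 v 9 months | 20% v 20% | 1.00 | 0.99 to 1.00 |
| 9 v 9 months | 30% v 15% | 0.88 to 0.89 | 0.98 to 1.03 |
| 9 v 9 months | 15% v 30% | 1.12 to 1.13 | 0.97 to 1.02 |
| 9 v 18 months | 30% v 15% | 0.49 | 0.49 censored, 0.55 death only |
| 9 v 18 months | 15% v 30% | 0.67 | 0.51 censored |

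**6. Scenario for power.** With 95 MSS patients, 12-month accrual, a 30-month cut-off and 9 v 18 months, simulated power is 82% if every progression is scored. If 20% per arm stop therapy before progression and that progression is not scored, power is 74% when they are censored at stopping. It is 54% when they stay event-free to the cut-off; deaths were not modelled, so this is an extreme case.

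**The case against.** The strongest reply is that the analysis text already settles the matter. Protocol 7.6.1, 10.4.1 and SAP 5.2 agree with one another and carry no on-therapy condition. The sentence in 5.5 sits in a section on how long treatment lasts and contains no censoring rule. Under the analysis text, progression after a toxicity stop, after resection or in a break counts, and so does death.

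Much of this stands. A reader might infer from 5.5 that these patients cannot have a PFS event and that their progressions go unscored. The documents do not support that. It would follow only if 5.5 governed, and even then death is an event in the calculation text. The censoring rule names only patients without progression, so it does not prescribe censoring someone who progressed off therapy. A reader might also take the remark in 10.1 that "it is not unlikely that some will be lost from the study before a valid PFS event has been reached" as an intention to discard off-therapy progressions. It speaks of patients lost from the study and says nothing about that.

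The scenarios should not be read as proof of bias from informative censoring either. Non-restart is random in steps 4 and 5, so those figures compare two end point definitions. With equal rates and no treatment effect the HR stays near 1.00. With more non-restart in control, the direction that FLOX exposure would suggest, the HR under the planned effect is 0.49 whether these patients are failures or censored.

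The reply does not remove the conflict. Read literally, the analysis text scores the planned week-24 break progression and contradicts the objective and the courses in 5.5. To match its own objective the sponsor must set aside break progressions that are followed by restart, and it then needs a rule for those that are not.

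**Conclusion.** The point holds as an unreconciled conflict between two definitions of the primary end point, with a missing scoring rule under the one that the objective and the 9 v 18 month illustration use. This much follows from the text alone: week 24 in both arms under one definition, weeks 40 and 80 under the other.

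The consequence for the HR is conditional. It needs 5.5 to govern and depends on how often each path occurs in each arm. The documents give none of those rates, so the medians, HRs and power figures above are scenarios and not estimates. They show that the scoring choice can move the control median by roughly 2.5 to 3 months (8.6 − 6.1 and 9.2 − 6.1) at an assumed 20% non-restart. They also show that the HR can move in either direction or hardly at all, depending on the split between arms. This should be corrected before database lock.

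**What to change.** State one governing definition, in the same words, in Protocol 5.5, 7.6.1, 10.4.1 and SAP 5.2. Strategy failure is the earliest of:

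1. progression during active study therapy;
2. progression in a break, or after stopping study therapy for any reason (toxicity, resection, decision), that is not followed by reintroduction of the assigned therapy within a pre-stated window, dated at that progression;
3. death.

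Only a break progression followed by actual reintroduction is set aside. This is a scoring rule and changes no treatment.

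Report PFS to first recorded progression or death as a sensitivity analysis. Reintroduction is an open-label decision, so the strategy end point will still depend in part on who is restarted.

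Reconcile Protocol 7.6.5, 7.7.3.2, 7.7.4 and the flow chart on disease assessment after study treatment stops, so that these progressions are captured on one schedule in both arms.

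The cost is a wording change in both documents, and possibly more imaging after treatment stops, depending on how the schedule is reconciled. Median PFS will be shorter than under an on-therapy-only definition: about 6 months against 8.6 to 9.2 in control in the 20% scenario. The 9-month assumption, and with it the event count, should therefore be checked against the definition chosen.
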